1. ABSTRACT

Chinese Americans are one of the fastest growing immigrant groups in the US, who suffer disproportionately high type 2 diabetes (T2D) burden and have poorly controlled T2D. Despite the well-documented T2D disparities in this minority group, limited work has been conducted to improve health outcomes in Chinese Americans. The goal of this Pathway to Independence Award (K99/R00) is to expedite the candidate's transition to an independent investigator who possesses focused expertise in development and evaluation of culturally and linguistically tailored and sustainable interventions to reduce T2D disparities in Chinese Americans. In the K99 phase of this award, the candidate will obtain critical training needed to accomplish this goal and will develop a short message service (SMS) intervention to improve T2D management in Chinese Americans. In the R00 phase, the candidate will utilize acquired skills to conduct a pilot randomized controlled trial to examine the potential efficacy of the SMS intervention. In the K99 phase, the candidate will also conduct pilot work to develop linguistically and culturally tailored SMS intervention content and to refine the intervention to be tested in the R00 phase. More specifically, the aims are to 1) characterize barriers and facilitators of glycemic control in Chinese Americans with T2D (Aim 1a); 2) develop culturally and linguistically tailored SMS intervention content (Aim 1b); and 3) assess the feasibility and acceptability of the SMS intervention in a pre-, post-test study (Aim 1c). In the R00 phase, the candidate will refine the SMS intervention based on the K99 pilot data and evaluate the proof-of-concept regarding its efficacy in a pilot randomized controlled trial among 60 Chinese Americans with T2D (Aim 2). Participants will be randomized to one of 2 arms (n=30 each): 1) wait-list control and 2) SMS intervention. Both groups will continue to receive standard of care treatment for their T2D. The SMS group will receive brief lifestyle counseling videos via SMS links. At the end of the study, the wait-list control group will be provided the opportunity to receive the SMS-based counseling videos. Measurements will be obtained at baseline, 3, and 6 months. The primary outcome is HbA1c and secondary outcomes include self-efficacy, diabetes self-management behaviors, dietary intake and physical activity behaviors. Linear mixed modeling will be used to examine the group and group by time interaction effects between the SMS intervention and wait-list control group. Findings from this R00 study will inform a larger full-scale R01 efficacy trial of the SMS intervention, and ultimately, establish the candidate's program of research focused on developing and testing sustainable interventions to reduce disparities in chronic disease outcomes in Chinese Americans. This project can serve as a program model for other chronic disease interventions in Chinese Americans that require lifestyle modification (e.g., prediabetes, hypertension), or for disparities research in other high-risk immigrant populations (e.g., South Asians, Hispanic Americans).

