3. METHODS AND PROCEDURES

3.1 Study Design

K99 Phase

Qualitative focus groups/interviews (N=20): We will conduct focus groups/interviews to understand barriers and facilitators of glycemic control in Chinese Americans with T2D and to develop culturally and linguistically tailored SMS intervention content.

Quantitative pre-, post-test evaluation (N=30): We will assess the feasibility and acceptability of the SMS intervention in a 3-month, single group pre-, post-test study among 30 Chinese Americans with T2D.

R00 Phase

Pilot RCT (N=60): Participants will be randomized to one of 2 arms (n=30 each): 1) wait-list control; or 2) SMS intervention. We will evaluate changes in HbA1c at baseline, 3-, and 6-months. In exploratory analyses, we will test mediators (e.g., self-efficacy, diabetes self-management behaviors, diet intake, and physical activity).

Rutgers Mental Health Pilot

Cross-sectional quantitative survey (N=133): We will contact the participants from K99, R00 phase (s18-00609), and FAMILY study (s19-01275) to ask whether they are interested in joining this mental health pilot and answering a few additional questions. Our target goal is 133. As of 9/28/2022, all participants from K99, R00 and FAMILY completed their assessments, intervention and participation with us. We will administer this mental health survey once this pilot modification was approved by the IRB. This will be a one-time survey administration because the goal of the pilot was to get a snapshot of the mental health burden in Chinese Americans with T2D. We are

not examining changes over time in mental health, thus, we will not repeat the survey at 3 or 6 months.

Qualitative focus groups (N=10-16): Guided by the NIMHD Research Framework,⁴¹ we will assess facilitators and barriers to accessing mental health services in Chinese Americans with T2D. We will explore factors on multiple levels, including individual, interpersonal, community, health system, and societal levels. We will select 10-15 participants based on their survey responses (who reported elevated stress, anxiety, or depressive symptoms) to join the focus groups (2 focus groups; 5-8 participants per group) to gain a deeper understanding of barriers to utilizing mental health services. We will also ask participants' preferences for mental health support (e.g., individual vs. group-based, in-person vs. phone vs. video-based).

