4.3.3 R00 Phase Pilot RCT Procedures

The R00 phase study is a pilot randomized controlled trial (RCT) of 6 months duration. Participants will be randomized to one of 2 arms (n=30 each): 1) wait-list control; or 2) SMS intervention. The study will include 3 measurement visits, baseline, 3, and 6 months. Patients will be paid \$30 for each measurement visit.

Upon receiving the referral list (interested patient's name and phone number) from the providers, the bilingual study staff will call the patient and provide more details about the study. If patients expressed interest in participation, the study staff will administer several screening questions over the phone. After eligibility is determined and verbal consent is obtained, we will collect baseline surveys over the phone and randomize them via a computer-generated randomization scheme with equal allocation to one of the 2 groups: 1) wait-list control; or 2) SMS.

Independent variable: randomization arm

Wait-list control group: All participants will continue to receive the standard of usual care for their T2D at their providers' office during the course of our study. At the end of the study, the wait-list control group will be provided the opportunity to receive the counseling videos delivered to them via SMS links.

SMS intervention: Participants in the intervention group will receive SMS-based video counseling, which include both educational and SCT-based behavioral content (see Table 1 below for a tentative outline of the intervention content). Given the system and personal barriers, we believe this SMS-based approach will improve access to culturally and linguistically tailored diabetes counseling. Additionally, this approach will allow participants to review the videos later on or share with their loved ones who often want to be supportive but do not know how. We will send 2 videos each week for a total of 12 weeks with each video about 5-10 minutes in duration. The videos will be sent via WeChat or regular text messages (SMS). We will contact participants mainly through phone calls from an NYU Langone Study Phone. WeChat will be only used to send the health education videos. No other communication will occur via WeChat. Our study team will remind participants at the beginning of the study and

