7. DATA ANALYSIS AND DATA MONITORING

7.1 Data Analysis

K99-phase Aim 1: All focus groups will be audio-recorded and transcribed verbatim into Microsoft Word. Atlas will be used to store, organize, retrieve, and analyze the qualitative data. Thematic analysis will be used to analyze qualitative data.⁶¹ To establish coding reliability, the RA and PI will independently code up to 10% of the transcripts and identify kappa coefficient.⁶² We will meet weekly to review definitions and assignment of codes, and resolve differences through consensus. If no agreement can be made, the study team will be consulted. The RA and PI will read all transcripts and develop an open coding schema based on emergent theses. We will present coding schemes to study team, discuss emergent themes, refine codes, and develop a codebook that consists of a list of categories and topics. Once all data have been coded based on the codebook, codes most relevant to the research questions will be subject to further analysis. For the quantitative data, a paired t-test will be used to determine pre-post change in HbA1c. Descriptive statistics will be used to summarize participants' satisfaction with the SMS intervention.

R00-phase Aim 2: We will employ the "intent to treat" (ITT) approach in analyses. We will perform a detailed descriptive analysis of all the data collected in the study. These preliminary descriptive statistics will be used to 1) check accuracy and completeness of inputted data, 2) describe univariate distribution of each variable at baseline, and 3) examine the associations between variables. We will also explore features of the data (e.g., amount and pattern of missing data, outliers, excess zeros, departures from distributional assumptions) to determine whether special techniques are needed.

Aim 2a: Establish the proof of concept regarding the efficacy of the SMS intervention for glycemic control in Chinese Americans with T2D. We will test whether the 2 groups are comparable on baseline sociodemographic, health characteristics, and levels of acculturation. If significant differences are found, we will include the variables as covariates in the models. Between group and group by time interaction effects will be examined graphically and via linear mixed modeling for HbA1c. Calculated effect sizes will be used for sample size estimation needed for a two-sided alpha of 0.05 and power of 0.80 for the larger scale R01 study.

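### Aim 2a does not say which HbA1c contrast is the efficacy estimate, at which visit, or how baseline HbA1c enters the model; one always baseline-adjusted contrast should be named and passed to the R01

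*Combined protocol and SAP*

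**What the plan says.** Section 7.1, Aim 2a, gives the primary analysis in one sentence: "Between group and group by time interaction effects will be examined graphically and via linear mixed modeling for HbA1c". The Abstract names the same two effects: "Linear mixed modeling will be used to examine the group and group by time interaction effects between the SMS intervention and wait-list control group". Neither place ranks them or names a visit.

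On timing, the Abstract says "Measurements will be obtained at baseline, 3, and 6 months" and Section 3.1 says "We will evaluate changes in HbA1c at baseline, 3-, and 6-months". Section 4.3.3 adds that the intervention stops well before the last visit: "We will send 2 videos each week for a total of 12 weeks". It also says that HbA1c is taken from the medical record, from routine tests done every 3 to 6 months.

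On covariates, Aim 2a compares the arms at baseline on sociodemographic factors, acculturation and health characteristics, and then: "If significant differences are found, we will include the variables as covariates in the models". HbA1c is named neither there nor in the covariate list of Section 4.3.3.

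On the use of the result: "Calculated effect sizes will be used for sample size estimation needed for a two-sided alpha of 0.05 and power of 0.80". The sentence assigns these to the R01, without naming a contrast or an SD.

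**The concern.** Proof of concept for efficacy is Primary Aim 2a, and the Abstract says that the findings will inform the R01. Both need one defined estimate. As written, the meaning of each named effect depends on a choice that the plan does not state.

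- **Baseline is an outcome row.** Sections 1 and 3.1 point this way. Group by time then compares changes from baseline and carries efficacy. A group effect averaged over all three visits mixes in a visit at which no effect is possible.
- **Only months 3 and 6 are outcomes.** The roles reverse. Group is the average efficacy effect, and group by time asks only whether that effect differs between the two visits. Baseline HbA1c then usually plays no part, because the only way in is a significant baseline test.

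The choice of term, visit and SD can therefore be made after results are seen, and it carries through to the R01 sample size. The plan also leaves unused the precision that baseline HbA1c, collected anyway, would give.

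**Working it through.** **Inputs from the documents.** 60 participants, 30 per arm (Section 4.3.3); visits at baseline, 3 and 6 months; two-sided 0.05 and power 0.80, for the R01 only (Section 7.1). The plan has no power, SD or effect figure for the pilot to reproduce.

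**Assumptions.** SD 1 at every visit, one common correlation r between visits (0.3 to 0.7), complete data, baseline tests at the 0.05 level.

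**1. Dilution.** With effects 0, d, d at the three visits, the three-visit group effect is (0 + d + d)/3 = 2d/3. If the effects at months 3 and 6 differ, it is still two thirds of their average.

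**2. Variance per participant for the 3/6-month average.**
- Unadjusted: (1 + r)/2
- Mean change from baseline: (1 + r)/2 + 1 − 2r = 1.5(1 − r)
- Baseline-adjusted: (1 + r)/2 − r²

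Adjustment saves r² against the unadjusted mean and (1 − r)² against mean change, so under these assumptions it is never worse than either. At r = 0.6 the variances are 0.80, 0.60 and 0.44.

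**3. 95% CI half-width** = t × SD × √(2/30), with t about 2.00. At r = 0.6, adjusted: 2.00 × 0.663 × 0.258 = 0.34.

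| r | Adjusted | Mean change | Unadjusted |
|---|---|---|---|
| 0.3 | 0.39 | 0.53 | 0.42 |
| 0.5 | 0.37 | 0.45 | 0.45 |
| 0.6 | 0.34 | 0.40 | 0.46 |
| 0.7 | 0.31 | 0.35 | 0.48 |

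The adjusted figures ignore chance baseline imbalance. That multiplies the variance by about 1 + 1/56, which widens the interval by about 1%.

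**4. R01 size per arm**, sustained 0.5 SD effect, r = 0.6: n = 2(1.96 + 0.84)²/d² = 15.7/d², plus about 1 for the t test.
- Adjusted: d = 0.5/0.663 = 0.754; 27.6 + 1, so 29
- Mean change: d = 0.5/0.775 = 0.645; 37.7 + 1, so 39
- Unadjusted: d = 0.5/0.894 = 0.559; 50.2 + 1, so 52

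**5. Adjusting only after a significant test.** Under randomisation a 0.05-level baseline test is significant in about 5% of trials. For a sustained 0.6 SD effect at r = 0.6 on the 3/6-month layout, simulated power is 72% with no adjustment, 75% with the conditional rule and 93% with adjustment always made. Mean change gives 84%.

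**6. Where the average does worse.** Suppose the effect is 0.6 SD at month 3 and zero at month 6, with r = 0.6. The adjusted average then has about 40% power, against 76% for the three-visit group-by-time test.

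**7. Missing month-3 values.** If they are missing at random and r = 0.6, the standard error of the adjusted average is 0.171, 0.180, 0.196 and 0.238 SD with 0, 25, 50 and 75% missing. Adjusted month 6 alone has 0.207. The two are equal at about 59% missing.

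**The case against.** The strongest reply is that this is a 60-person proof-of-concept pilot with no stated pilot alpha, and that on the likelier layout group by time already compares changes from baseline. Both points stand. They rule out several stronger readings that a reader might infer.

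- **That the plan adjusts for baseline HbA1c only if it differs significantly.** The text does not say this. HbA1c would have to count as a health characteristic. If it does not, the plan gives it no covariate route at all.
- **That baseline is ignored, so adjustment narrows the interval from 0.46 to 0.34 SD.** The 0.46 belongs to a layout with months 3 and 6 only, which no section states for HbA1c. The mention of 3 and 6 months under Aim 2b covers other outcomes. Against mean change the gain is 0.40 to 0.34 SD at r = 0.6.
- **That the R01 would be sized from the diluted three-visit group effect.** Nothing says that this term would be used.
- **That the conditional rule or the two unranked effects inflate error.** The simulated type I error of the conditional rule was 3.8% at r = 0.6, so its cost is lost precision. The plan sets no error rate for the pilot that two tests could breach.

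The reply does not settle which term, visit and SD supply the efficacy estimate and the R01 effect size, or why baseline HbA1c should not always be used.

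**Conclusion.** The point holds in this form: the efficacy contrast, its visit, the handling of baseline HbA1c and the effect size for the R01 are all unspecified, and the only stated covariate route is a significance test. It should be fixed. This is more than missing detail, because a better method is available from data already collected. The baseline-adjusted 3/6-month average is more precise than both mean change and the unadjusted mean at every correlation from 0.3 to 0.7.

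The gain over mean change shrinks as correlation rises: 0.14 SD in half-width at 0.3 and 0.04 at 0.7. Over the unadjusted mean it grows, from 0.03 to 0.17. All sizes rest on assumed equal SDs, a common correlation and complete data. The entry threshold of HbA1c 7% or more and the irregular timing of routine tests could make the true SDs and correlations differ. No contrast is best for every pattern of effect over time. The main consequence is an ambiguous pilot estimate and R01 sample size, not a false confirmatory claim.

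**What to change.** Replace both the significance-based covariate rule and the Aim 2a model sentence with:

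> HbA1c at 3 and 6 months will be analysed in a linear mixed model with arm, categorical visit, arm by visit, and baseline HbA1c always included (as a covariate, or as an outcome with a common mean across arms). Other covariates will be fixed in advance and not chosen by baseline significance tests. The primary estimate is the SMS minus control difference averaged over 3 and 6 months, with its 95% CI; the single-visit differences and the arm-by-visit test are supportive. This estimate, its matching SD and its CI will inform the R01. A group effect that includes the baseline visit will not be used as evidence of efficacy.

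The average is chosen on design grounds: it uses both planned post-baseline visits, one near the end of the 12 weeks of videos and one about three months later. The choice must not depend on observed missingness or on HbA1c by arm.

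No new data are needed. There are two costs. Power is lower than for the interaction test if the effect has gone by month 6. Half the weight also falls on month-3 values from routine tests done every 3 to 6 months, and the missing-data figures above do not cover values missing for reasons linked to glycaemic control.

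Section 3.1 states: "As of 9/28/2022, all participants from K99, R00 and FAMILY completed their assessments, intervention and participation with us". The change must therefore be recorded as made after data collection, with a statement of whether HbA1c by arm had been seen. If it had, the contrast should be labelled post hoc.

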3.3. Characteristics of the Research Population

Phase 1: K99 Phase Feasibility Study Inclusion criteria: To be eligible for the study, participants must: 1) self-identify as Chinese Immigrant or Chinese American; 2) be 18-75 years old, 3) be able to speak and understand Mandarin; 4) self-report a diagnosis of T2D; 5) know how to do a finger stick blood sugar test; 6) be willing to do a finger stick blood glucose test for each study visit; 7) baseline HbA1c $\geq 7\%$; 8) be currently using WeChat; 9) be willing to receive WeChat messages regarding T2D management, 9 10) express strong interest and confidence in finishing watching 2 diabetes videos each week for a total of 12 weeks; 11) be motivated to make lifestyle changes to control their diabetes.

Phase 1: K99 Phase Feasibility Study Exclusion criteria: Individuals will be excluded from participation if they meet any of the following:(1) unable or unwilling to provide informed consent; (2) unable to participate meaningfully in the intervention (e.g., uncorrected sight and hearing impairment); (3) unwilling to accept randomization assignment; (4) pregnant, plans to becomes pregnant in the next 6 months, or who become pregnant during the study, or (5) breastfeeding or

(6) live in a facility or other health care setting where they have no control over diabetes self-management.

Phase 2 R00 Phase pilot RCT Inclusion criteria: To be eligible for the study, participants must: 1) self-identify as Chinese Immigrant or Chinese American; 2) be 18-70 years old, 3) be able to speak and understand Mandarin; 4) self-report a diagnosis of T2D; 5) baseline HbA1c $\geq 7\%$; 6) be currently using WeChat or text messages; 7) be willing to receive WeChat or text messages regarding T2D management, 8) express strong interest and confidence in finishing watching 2 diabetes videos each week for a total of 12 weeks; 9) be motivated to make lifestyle changes to control their diabetes; 10) be willing to wear ActiGraph for 8 days.

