| 12 | Review of lifestyle recommendations | Problem solving: Anticipating high-risk situations |

Procedures: The study will include 3 measurement phone calls, baseline, 3, and 6 months. Patients will be paid \$30 for each measurement call. Due to COVID-19, all data will be collected over the telephone. Each survey calls will include audio/Video recordings if verbal consent from the study participants was obtained. For participants randomized to the SMS intervention group, we will reimburse \$5 each week to each participant for cell phone data usage if they finish viewing both of the sent videos for that week. Given that we will send videos over a total of 12 weeks, participants may expect to receive a range of \$0-\$60 ($=\$5*12$) depending on the number of weeks they have completed the videos. We will also provide \$60 to control participants if they finish all study related procedures at 3 months assessment.

Study Variables

covariates

[figure not shown]

Figure 1. Conceptual Model

Primary & Exploratory Outcomes

Primary outcome: HbA1c: As part of the usual care, patients with T2D receive a HbA1c blood test at their doctors' office every 3-6 months. To minimize participants' burden, we will not conduct additional blood tests for this study. Instead, we will abstract the HbA1c testing results from the medical record at the participant's health care facility. Once we obtain the consent from participants, we will contact their doctors' offices for HbA1c results.

Secondary outcomes: Consistent with our conceptual model (Fig. 1), we will also measure self-efficacy, diabetes self-management behaviors, dietary intake, and physical activities at each time points (baseline, 3-, and 6-months). All of these scales have been used and validated in the Chinese population.

1. **Self-efficacy:** We will use the well-validated Stanford Diabetes Self-Efficacy Scale⁴² to measure participants' confidence to manage T2D. This instrument contains 8 items and asks participants to rate their confidence level in performing specific self-management behaviors, using 10-point Likert scale ranging from 1 (not at all confident) to 10 (totally confident).

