2. **Diabetes Self-Management Behaviors:** We will administer the adapted Summary of Diabetes Self-Care Activities (SDSCA) measure⁴³ to assess participants' adherence to diabetes self-management behaviors. This scale consists of 13 items and asks participants to describe their diabetes self-care activities over the past 7 days.
3. **Dietary Intake:** Informed by a previous study in Chinese Americans,⁴⁴ we will use the adapted Mediterranean Dietary Screener⁴⁵ to estimate dietary intake behaviors in our participants at baseline, 3- and 6-months.
4. **Physical Activity:** We will use the International Physical Activity Questionnaire (IPAQ)^{46,47} short version to assess the frequency and duration of various physical activities undertaken by adults over the past 7 days. This scale will provide an estimate of the number of minutes per week participants engage in each category of physical activity (e.g., vigorous, moderate, and mild intensity). We will also use the ActiGraph to objectively measure physical activity and sleep. Our study staff will distribute and collect the device to participants once they are eligible for the study. Once we receive the device, we will download the data.

Covariates: Sociodemographic, health characteristics, and acculturation. We will use a sociodemographic questionnaire to collect basic information about the participant such as age, gender, education, income, duration of residence in the US, health insurance, the diabetes medication regimen, duration of T2D, and medical history. Informed by prior literature, we will also include surveys to measure Health Beliefs, Diabetes Knowledge, Diabetes Distress, Social Support, Mental Health, the Impact of COVID-19, and memory test, which also play essential roles in diabetes management.

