Exploratory Aim 2b: Explore the potential effects of the SMS intervention on psychosocial and behavioral factors in glycemic control. For continuous secondary outcome variables (self-efficacy, adherence, and dietary data), linear mixed modeling will be used to examine the group and group by time interaction effects for each outcome at 3- and 6-months. For the physical activity data, we will use a GEE logistic model to examine whether there are group differences in the proportions of participants achieving 150 minutes/week of physical activity at any level of intensity and at a moderate- or greater intensity level.

Rutgers Mental Health Pilot

Aim 2c: Examine current mental health burden and psychosocial support and how they are related to diabetes self-care behaviors and glycemic control in Chinese Americans with

T2D. We will use descriptive statistics to summarize mental health burden and psychosocial support in Chinese immigrants with T2D. We will describe the percent of the sample who has elevated stress, anxiety and depressive symptoms and the current social support and coping strategies. We will also use correlation to examine the relationships between the mental health burden and diabetes self-management behaviors and HbA1c (measured in R00 study).

Aim 2d: Characterize barriers to accessing mental health services and understand needs and preferences in Chinese Americans with T2D. Similar to the analytic approach used in the K99 Aim 1 analyses, all focus groups will be audio-recorded and transcribed verbatim into Microsoft Word. Atlas will be used to store, organize, retrieve, and analyze the qualitative data. Thematic analysis will be used to analyze qualitative data.⁵⁹

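### Physical activity (exploratory Aim 2b) gets only a GEE logistic model on a 150 minutes/week cut; a baseline-adjusted rank analysis of IPAQ minutes, averaged over 3 and 6 months, would be a cheap addition beside it

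*Combined protocol and SAP*

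**What the plan says.** Section 4.3.3 lists physical activity among the secondary outcomes and plans to measure "dietary intake, and physical activities at each time points (baseline, 3-, and 6-months"). The instrument is the IPAQ short form: "This scale will provide an estimate of the number of minutes per week participants engage in each category of physical activity". An ActiGraph is used as well.

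Section 7.1, Exploratory Aim 2b, treats the other outcomes on their own scale: "For continuous secondary outcome variables (self-efficacy, adherence, and dietary data), linear mixed modeling will be used", with group and group-by-time effects at 3 and 6 months. Physical activity is not in that list. For it the plan says "we will use a GEE logistic model to examine whether there are group differences in the proportions of participants achieving 150 minutes/week", and the cut is applied at two levels: "150 minutes/week of physical activity at any level of intensity and at a moderate- or greater intensity level". That sentence does not give the visits, the baseline handling or the source of the minutes, although the intensity wording fits the IPAQ categories.

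Two more general statements bear on the point. The abstract says "Linear mixed modeling will be used to examine the group and group by time interaction effects between the SMS intervention" and the control group, without tying this to an outcome. The opening of the Aim 2 analysis in section 7.1 plans descriptive statistics, then a look at missing data, outliers, surplus zeros and distributional problems, to decide whether other methods are required.

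**The concern.** A measure in minutes is reduced to yes or no in a 60-person pilot. Under the cut, a rise from 10 to 140 minutes counts as no change, while a rise from 145 to 155 counts as a success. Change wholly above or wholly below 150 minutes is invisible.

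Physical activity is a secondary outcome and, in section 3.1, a candidate mediator of the HbA1c effect. The pilot exists to inform a larger trial, so a behavioural signal that is present in the collected data but lost in the analysis has some cost. The cost is bounded, because Aim 2b is exploratory.

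**Working it through.** The plan has no figure to reproduce: it gives no power, effect size, spread or share above 150 minutes for this outcome.

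**Inputs from the documents.** 60 participants, 30 per arm, equal allocation (section 4.3.3); visits at baseline, 3 and 6 months; cut at 150 minutes/week. Two-sided alpha 0.05 appears in section 7.1 only for sizing the later trial and is borrowed here.

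**Assumed inputs.** A latent normal activity level with correlation 0.5 between visits; a 0.5 SD shift in the intervention arm at both follow-ups; 20-40% reporting zero minutes, with lognormal minutes otherwise; 30%, 50% or 80% of controls meeting the cut; no dropout.

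**1. Information kept by a cut.** For a normal variable with share p above the cut, this is φ(z)²/[p(1−p)]:
- p = 0.5: 0.637
- p = 0.3 or 0.7: 0.576
- p = 0.2 or 0.8: 0.490

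**2. One visit, like for like, no baseline adjustment.** With 50% of controls above the cut, a 0.5 SD shift gives Φ(0.5) = 69.1% in the intervention arm. Comparing 50% with 69.1% at 30 per arm has power 0.32. For ranks, the effective shift is 0.5/√(π/3) = 0.489, and power is Φ(0.489 × √15 − 1.96) = Φ(−0.07) = 0.47.

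**3. Both follow-ups, adjusted for baseline.** Simulation with 1000 runs per row, so Monte Carlo error is about ±3 points; SD of log minutes 1.0. The rank analysis uses the mean of the 3- and 6-month ranks, adjusted for baseline rank. The GEE uses both follow-ups with baseline status as a covariate. That is a favourable reading of the planned model: in a setting with 50% meeting the cut and 20% zeros, it had 52%, against 24% for a group-by-time test over three visits and 27% for a group main effect over three visits.

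| Zeros | Controls meeting cut | Averaged ranks | GEE on cut | Difference (points) |
|---|---|---|---|---|
| 20% | 30% | 73.7% | 54.3% | 19.4 |
| 20% | 50% | 73.4% | 55.2% | 18.2 |
| 40% | 30% | 67.4% | 51.9% | 15.5 |
| 40% | 50% | 69.2% | 52.7% | 16.5 |
| 20% | 80% | 73.4% | 36.7% | 36.7 |

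Repeat runs put the GEE at about 49-55% for 30-50% meeting the cut and 33-37% for 80%. With no effect, the rank analysis rejects in 4.8-5.1% of runs. With 20% dropout (50% meeting the cut) the figures are 67% and 47%. With a 0.3 SD shift both are weak: 33-34% for ranks, 21-24% for the GEE.

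**4. Which contrast carries the gain.** A rank test at a single visit has about 50-57% power, level with the two-visit GEE when 30-50% meet the cut. The group-by-time term rejects in only 3-5% of runs, because the shift is the same at both follow-ups and there is nothing for it to detect. In a model with a group-by-time term under reference coding, the group coefficient is a one-visit effect. The averaged contrast therefore has to be named.

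**5. Why ranks and not raw minutes.** At SD of log minutes 1.5 and 30-50% meeting the cut, raw minutes reach 36-40%, below the GEE's 51-54%.

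**6. Counter-case.** One visit, 3000 runs, 50% of controls above the cut, and the intervention only lifts people from just below the cut to just above it. The binary comparison has power 0.24-0.41 and ranks 0.05-0.07.

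**The case against.** The binary model is valid, easy to read and tied to a recognisable target, and the outcome is exploratory. A rank effect is not a difference in minutes. All of this stands, and it is why this is an optional improvement and not an error.

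It can be said that the plan already covers the minutes. The abstract's mixed-model sentence follows a list of secondary outcomes that includes physical activity. But it assigns no model to any outcome, and section 7.1, the specific text, leaves physical activity out of its list of continuous outcomes. The clause in section 7.1 on zeros and distributional problems does allow an analysis of minutes, but it specifies none.

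The strongest objection concerns the shape of the effect. Every favourable figure assumes a general shift in activity. The documents say nothing about shape, and step 6 shows that the ranking of the two methods can reverse. That stands, and it rules out replacing the GEE.

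A reader might infer more than the documents support:
- That the GEE is wrong or should be dropped. Neither the text nor the figures show that.
- That any continuous or rank analysis would do better. A single-visit rank test and an analysis of raw minutes need not.
- That the pilot would become well powered for this outcome. At a 0.3 SD shift it would not.

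**Conclusion.** The point holds in limited form. Minutes are planned at three visits, and the only between-group model named for them is a dichotomised one. If activity shifts in general by 0.5 SD at both follow-ups, a baseline-adjusted rank analysis averaged over 3 and 6 months gains roughly 15 to 20 points of power when 30-50% of controls meet the cut, and more when most already do. These figures depend wholly on the assumed effect shape, correlation and share of zeros. They do not apply to a single-visit contrast or to an effect confined to the cut. This is a cheap improvement that the team could make.

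**What to change.** In section 7.1, Exploratory Aim 2b, add one exploratory between-group analysis:
- **Measure.** IPAQ moderate-or-greater minutes per week as the lead, total minutes as supportive. Naming IPAQ also settles the source of the minutes.
- **Model.** At each visit, rank minutes over both arms and divide by the number observed. Fit the linear mixed model already used for the other Aim 2b outcomes to the 3- and 6-month ranks, with group, time, group-by-time and baseline rank.
- **Reported contrast.** The group effect averaged over 3 and 6 months.
- **Description.** Medians and quartiles in minutes by arm and visit, since the rank effect cannot be read in minutes.

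Keep the 150-minute GEE, and state that it is fitted to the 3- and 6-month visits with baseline status as a covariate.

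Section 3.1 says R00 assessments were complete by 9/28/2022. Date the change, and label the analysis post hoc if outcome data had been seen.

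The cost is a few sentences and one or two more exploratory tests, with no new data. The downside is an effect measure that is harder to interpret than a proportion, which is why the medians and the 150-minute proportions stay beside it.
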